with his or her family, friends, co-workers, doctor, etc. To minimize this risk, participants will be asked not to share any personal information shared within the group sessions with outside sources. During the consent process, participants will be asked to consent to the rules of confidentiality and will be informed that the research team cannot 100% guarantee that all participants will maintain confidentiality. Participants will also be made aware that confidentiality would be broken if an individual seems at risk of harming themselves or others, in order to obtain appropriate care for the person. Study staff will monitor the intervention groups to determine whether any information raises questions about safety risk.

The PI will oversee all data collection and analysis and will ensure the integrity of the project. As noted above, study data will not be linked to any identifying information; rather study ID numbers will be assigned and used to identify participants. All study forms and data will be stored in an access-restricted database, in which only trained study staff will have access to.

SENDING SPECIMENS/DATA TO RESEARCH COLLABORATORS OUTSIDE PARTNERS

Specimens or data collected by Partners investigators will be sent to research collaborators outside Partners, indicate to whom specimens/data will be sent, what information will be sent, and whether the specimens/data will contain identifiers that could be used by the outside collaborators to link the specimens/data to individual subjects.

De-identified dried blood spot samples will be sent to our collaborator [name] at Northwestern University for storage and/or processing. All samples will be labeled with the patient ID, date of collection, time of collection, and time point (baseline, post-intervention, 3-month follow-up). We will place a freeze pack inside of an insulated shipping container and will place sealed plastic bags containing the samples into a box. We will seal the box tightly with tape and ship specimens via courier to [name] in Health Lab at the Northwestern University Feinberg School of Medicine.

[name] will securely store the samples in his locked lab at Northwestern before bringing them for processing to his collaborator [name] at the Laboratory for Human Biology Research at Northwestern University. The blood samples will not contain identifiers that could be used by the outside collaborators to link the data to individual subjects; they will be labeled with participants' study ID numbers and not any personally-identifying information, and only Partner's study staff will have access to the data file linking participant's personal information to their study ID number.

Specifically address whether specimens/data will be stored at collaborating sites outside Partners for future use not described in the protocol. Include whether subjects can withdraw their specimens/data, and how they would do so. When appropriate, submit documentation of IRB approval from the recipient institution.

Blood samples will not be stored for future use not described in the protocol. Once blood samples are processed for the purposes described in this protocol, they will be destroyed.

RECEIVING SPECIMENS/DATA FROM RESEARCH COLLABORATORS OUTSIDE PARTNERS

When specimens or data collected by research collaborators outside Partners will be sent to Partners investigators, indicate from where the specimens/data will be obtained and whether the specimens/data will contain identifiers that could be used by Partners investigators to link the specimens/data to individual subjects. When appropriate, submit documentation of IRB approval and a copy of the IRB-approved consent form from the institution where the specimens/data were collected.

We will not receive blood samples from collaborators outside of Partners.

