learn about cardiac health. We will hold two intervention cohort groups that may be run concurrently or sequentially. Participants involved in the intervention will be asked to complete a brief survey following each session. Within one week before and after the intervention and 3-months post-intervention participants will be asked to complete a series of questionnaires and provide self-collected blood samples. Upon completion of the intervention participants will complete an audio-or video recorded exit interview (approximately 30 minutes). Participant characteristics, inclusion/exclusion criteria and/or intervention design will not differ between the two cohorts.

Inclusion criteria:

1. Lifetime ACS per medical record and/or patient confirmation
2. Current elevated depression symptoms (PHQ-9 \geq 5)
3. Age 35-85 years
4. Access to high-speed internet

Exclusion criteria:

1. Active suicidal ideation or past-year psychiatric hospitalization (per patient report and/or medical record review)
2. Non-English-speaking
3. Cognitive impairments preventing informed consent per medical record review and/or cognitive Screen \leq 4
4. Patient deemed unable to complete the study protocol or has a condition that would likely interfere with the study

There are no exclusion criteria with respect to ethnicity or socioeconomic status.

Briefly describe study procedures. Include any local site restrictions, for example, “Subjects enrolled at Partners will not participate in the pharmacokinetic portion of the study.” Describe study endpoints.

Recruitment: Participants will be recruited in several ways. First, patients will be identified using the MGH Research Patient Data Registry (RPDR). IRB approval will be obtained to search the RPDR for patients who meet eligibility criteria, including both RODY and non-RODY patients (Research Options Direct to You; i.e., patients who have agreed to be contacted directly about research studies). Non-RODY patients will be sent an opt-out letter from our team and their cardiologist. RODY patients will be sent an opt-out letter by the study team. Patients will have the option to opt-out via phone or email. To address security issues related to email communication, participants will be informed about security in the opt-out letter itself via inclusion of the following text:

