Adapted MBCT intervention. The intervention will be based on Mindfulness-Based Cognitive Therapy (MBCT), an evidence-based, manualized protocol for treating depression symptoms. We will use the existing manualized protocol with adaptations for ACS patients. Following consent, participants will be enrolled in one of two MBCT intervention cohorts. Assignment to each cohort will be based on timing and/or participant scheduling preferences. Participants will be expected to participate in 8-weekly, 1.5-hour virtual sessions, in conjunction with approximately 30 minutes of at-home daily practice. A licensed mental health provider (e.g., LICSW, PhD) trained in the MBCT protocol will deliver the intervention. The interventionist will meet formal training guidelines for MBCT delivery including participation in MBCT workshops, experience leading ≥ 2 MBCT groups with mentorship, and >1 year of experience with group psychotherapy. The interventionist will receive ongoing supervision and feedback from the PI. The MBCT intervention will not be delivered clinically; it is a psycho-educational intervention. We will also send audio recordings used for home mindfulness practice via a send secure Partners email or via Dropbox to participants throughout the intervention.

Intervention delivery. We will deliver the intervention using Zoom, a secure, HIPPA compliant video-conferencing software amenable to study procedures, which we have used successfully in prior studies to deliver mindfulness interventions to other patient populations. Participants will be informed during consent procedures that the videoconferencing system uses a secure, HIPPA-compliant software program. We will explain that although we will do our best to ensure confidentiality on our end and ask group members to not share information outside of the group, we cannot guarantee that other group members will not share the content of the group. Participants will be advised to wear headphones and sit in a quiet place to protect their own and other group members' privacy.

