Data collection. Study assessments include a battery of self-report surveys administered at baseline, post-intervention, and 3-month follow-up; session satisfaction surveys administered after each intervention session; post-intervention individual exit interviews (conducted via telephone or videoconference); blood spot samples self-collected by participants at baseline, post-intervention, and 3-month follow-up (submitted to the research team via paper mail); and home practice logs submitted between each intervention session. Surveys and home practice logs may be completed via REDCap, email, paper mail, phone, or videoconferencing depending on patients' preferences. Data collection will also consist of viewing and extracting data from the EHR of enrolled participants to assess medical and demographic variables (e.g. medical diagnoses, medications, cardiac rehab attendance). See Figure 1 for an overview.

[figure not shown]

Figure 1. Overview of open pilot data collection procedures

Survey measures. The self-report survey measures will be administered within approximately one week before and after the intervention and at 3 months post-intervention. This battery will include the following validated self-report surveys: PHQ-9 (depression symptoms), FFMQ-15 (mindfulness), PANAS-PA (positive affect), RRS (rumination), SOFI (self and other compassion), IRI (empathy), MOS-SAS (adherence), one item from the SF-12 (health-related quality of life), PROMIS-PF (physical function), HADS (anxiety and depression), and CES (resilience). The baseline survey will also include the Expectancy Questionnaire (EQ) to assess expectations about the utility of the intervention. The post-intervention survey will also include a group cohesiveness measures to assess perceived connection with other group members as well as intervention satisfaction questions to assess acceptability. The 3-month follow-up survey will include questions about continued mindfulness practice. The baseline survey, post-intervention survey and post-intervention survey will all include questions related to COVID-19. All three survey batteries are included in the IRB submission.

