Post-session surveys. The post-session surveys will be administered immediately after each of the 8-sessions and will assess participants' perceptions, and likes and dislikes, of specific intervention components. Prior to each session participants will be asked to email, mail, or complete via REDCap a record of their at-home mindfulness practice since the previous session. The post-session surveys and home practice log are included in the IRB submission.

Exit interview. Upon completion of the intervention, participants will be asked to complete a 30-60 minute exit interview via phone or video conference. These interviews will be audio- and/or video-recorded for transcription.

Dried blood spots. Within one week before and after the intervention and 3-months-post intervention, participants will be asked to provide self-collected whole dried blood spots to assess IL-6, CRP, and TNF- α using a minimally invasive finger skin prick technique, which involves pricking the finger with a lancet, milking the finger to produce 5-10 drops of blood onto filter paper, allowing the blood spots to dry, and mailing it to the study team at MGH in a secure envelope. Prior to the start of the intervention, an RA will guide the participant in self-collecting blood samples via a videoconference call, phone call, and/or in person (per the participant's preference). Participants will be sent a video link for a guided demonstration of the procedure and/or written instructional handouts. The RA will ask the participant a series of questions to gauge understanding, provide corrective feedback, and answer any questions the participant might have before proceeding to guide the participant in the procedure. Skin prick procedures are safe for patients on beta-blockers and anticoagulants. Participants may also receive written instructional materials.

Participants will be asked to allow the sample to dry overnight, document the date the sample was taken on the filter paper, and mail it to the study team at MGH the next morning. Samples

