will be received by the RA, who will mark the date of receipt in the study database. Samples can be in ambient air for up to 2 weeks without degradation. We will ask participants to mail the samples within 24 hours of taking them to minimize the time samples are in ambient air. If samples are received beyond 2 weeks of the date indicated on the filter paper, we will ask participants to provide another sample, and participants will be made aware of this possibility in the consent form. Once received, the RA will bring the samples to be stored in a -20°C freezer in the MGH Clinical Research Center lab or mail them to our collaborator at the Laboratory for Human Biology Research at Northwestern University for storage and processing. Blood spots can be frozen at this temperature for several years without degradation.

When initially mailing the blood spot kit to participants, the RA will indicate the participant's study ID number on the filter paper. Participants will be informed not to write any personally identifying information on the filter paper. This will keep the blood samples de-identified.

Collecting whole blood spots with filter paper has been used in hospitals for decades to collect blood from newborns, and it has proven to be a safe and effective means for collecting and transporting samples in several large NIH-funded field-based studies. The Centers for Disease Control and Prevention have maintained independent quality control efforts and have reported that these approaches can achieve the same level precision and reproducibility of standard blood collection methods. Our collaborators at Northwestern University have pioneered this technique as leaders in the development, validation and application of whole dried blood spots as a convenient means for collecting, transporting, and processing blood samples from community settings and mind-body intervention research including clinical trials.

Measured Outcomes: The primary outcomes are feasibility and acceptability of the intervention and research procedures. Study staff will record all feasibility outcomes throughout recruitment, screening, enrollment, and the intervention, data collection, and follow-up phases.

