As with any study, there is the risk of a breach of confidentiality; these risks will be minimized by using participant ID numbers rather than identifying personal data on study documents, and by using locked cabinets/offices and password-protected databases to store personal information. Only study staff (the PI and the research assistant entering data) will have any access to personally identifiable information about participants, and such access will be limited only to information necessary to complete study tasks. The process of submitting blood spot samples via paper mail may pose a risk of samples getting lost in the mail. To minimize this risk, participants will be asked to inform the RA when they mail the sample, and the RA will contact the patient to let them know when the sample has been received. These samples will only be labeled with the participant's study ID number and not with any personally-identifying information.

Participants will be advised to wear headphones and sit in a quiet place during each virtual intervention session. We will instruct participants to maintain the confidentiality of group members by not discussing any events or information associated with other group members outside of the group. Added attention will be taken during the informed consent process to explain this risk to participants.

The audiotaped or video-taped recordings of the individual exit interviews and MBCT intervention sessions will be identified only with the participant's study ID number or intervention group/session number (with this number linked to identifying information that is kept in a password-protected database). These recordings will be stored in a password-protected folder on Partners' secure network, and will be destroyed 7 years following the completion of the study.

Describe explicitly the methods for ensuring the safety of subjects. Provide objective criteria for removing a subject from the study, for example, objective criteria for worsening disease/lack of improvement and/or unacceptable adverse events. The inclusion of objective drop criteria is especially important in studies designed with placebo control groups.

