Participants will be reimbursed using the Partners Forte Payment system. Forte Payments is a cloud-based application that provides subjects with a reloadable Visa card that is credited with fixed stipends following specified data collection points. Participants will be informed of Forte policy via the informed consent form. After agreeing to participate in the study, participants will also be asked to sign a “Forte Participant Payment Card Acknowledgement of Receipt” form, to certify their understanding of Forte Payment policies. The form will require the subject to print and sign their name and provide their social security number. When mailing “Forte Participant Payment Card Acknowledgement of Receipt” forms is not an option (e.g. due to COVID work restrictions), participants will be asked to complete the form electronically via REDCap. Similar to the electronic consent process detailed below, study staff will email participants a link to an electronic version of the form. Participants will be given time to review Forte guidelines, and when ready will review and electronically sign the “Forte Participant Payment Card Acknowledgement of Receipt” form with study staff over the phone. Participants will then be provided with the option of receiving a mailed copy of the completed form through send secure email or through paper mail. All paper versions of the Forte acknowledgement forms will be stored in a locked, study cabinet.

Participants will be remunerated up to \$145 via a reloadable debit card. Participants will receive \$10 for each survey battery completed within one week before and after the intervention and 3-months post-intervention (e.g. up to \$30 total). Participants will receive \$5 for each of the 8-post session survey completed (e.g. up to \$40 total). Participants will receive \$15 for the completion of an individual exit interview. Participants will receive \$20 for each of the three dried blood spot sample collections (e.g. up to \$60 total). Participants will be remunerated via their reloadable debit card directly following their completion of the aforementioned study procedures. Participants will participate in the intervention free of cost.

For guidance, refer to the following Partners policies:

Recruitment of Research Subjects

<https://www.partners.org/Assets/Documents/Medical-Research/Clinical-Research/Recruitment-Of-Research-Subjects.pdf>

Guidelines for Advertisements for Recruiting Subjects

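### Does the two-week late-receipt rule for blood spots leave replacement samples that the plan cannot place or count?

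*Protocol*

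**What the plan says.** The Dried blood spots section sets the timing: "Within one week before and after the intervention and 3-months-post intervention, participants will be asked to provide self-collected whole dried blood spots". The design summary under Research Design and Methods gives the same timing for surveys and samples together. The Survey measures paragraph is slightly looser for questionnaires: "administered within approximately one week before and after the intervention and at 3 months post-intervention". The course itself is weekly: "Participants will be expected to participate in 8-weekly, 1.5-hour virtual sessions".

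Participants are asked to dry the sample overnight, write the collection date on the paper and post it the next morning, within 24 hours of collection. The research assistant logs the date of receipt. The late rule follows: "If samples are received beyond 2 weeks of the date indicated on the filter paper, we will ask participants to provide another sample". The section says that participants are told of this possibility in the consent form.

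Under the heading on sending specimens outside Partners, every sample is labelled with its collection date and time and with one of three time points. Remuneration is paid "for each of the three dried blood spot sample collections". Against loss in the post, "participants will be asked to inform the RA when they mail the sample", and the assistant confirms arrival.

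Measured Outcomes sets the blood-spot benchmarks: at least 75% submitted at baseline and at post-intervention, at least 60% at follow-up, and 80% of adequate quality. SAP section 6.2 lists the matching percentages as descriptive statistics. Under Monitoring and Quality Assurance, the outside laboratory reports which samples were not good enough to assay.

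**The concern.** The collection window is one week and the trigger for a redraw is more than two weeks, so a redraw cannot fall in the window that its in-window original met. A sample meant to be pre-intervention would be taken after sessions had begun, and a post-intervention sample would be taken more than a week too late.

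The plan has three labels, three payments and three submission rates, with no stated place for a fourth sample. If a redraw were filed under baseline, it could count as both submitted and adequate without being a pre-intervention sample, because the laboratory's quality report does not mention timing. Blood-spot procedures are one of the three components of Specific Aim 1 and are meant to inform a later pilot RCT. A reader of the two planned rates could then overestimate how well mailed collection delivers samples from before treatment.

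**Working it through.** No stated figure in the plan needs reproducing. The check is a day count, followed by a look at the rates.

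**Inputs.** Window: 7 days on either side of the intervention (Dried blood spots). Trigger: receipt more than 14 days after the written date, so the earliest redraw is collection day + 15 (same section). Sessions: eight, weekly, on days 0, 7, ..., 49 (Adapted MBCT intervention). Enrolment: about 20 (Research Design and Methods).

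**Baseline** (day 0 = first session; window −7 to 0):
- Original on day −7: −7 + 15 = day +8, with sessions on days 0 and 7 already held (2 of 8).
- Original on day 0: 0 + 15 = day +15, with sessions on days 0, 7 and 14 already held (3 of 8).
- Days past the window: 8 to 15.

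**Post-intervention** (day 0 = last session; window 0 to +7):
- Original on day 0: day +15, which is 15 − 7 = 8 days past the window.
- Original on day +7: day +22, which is 22 − 7 = 15 days past the window.

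**Sensitivity.** If the trigger is read as day 14 itself, the miss is 7 to 14 days. If the baseline window is stretched to two weeks, −14 + 15 = day +1, still after the first session. A baseline redraw on or before day 0 needs an original on day −15 or earlier, which is itself out of window. The mismatch therefore holds for every in-window original and only for those. The 3-month sample has no stated window, so the check does not apply to it.

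**Effect on the rates.** At 20 participants each sample is 100/20 = 5 percentage points, and the 75% benchmark is 15 samples. Suppose 16 participants return a baseline sample and one of these arrives late; both counts are assumptions, because the documents give no late rate.
- Late original counts as submitted, redraw adds nothing: 16/20 = 80%.
- Both samples enter numerator and denominator: 17/21 = 81%.
- Neither counts: 15/20 = 75%, still at the benchmark. With two such participants: 14/20 = 70%, below it.

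The last reading is the only one that lowers the rate, and it is strained. A sample that arrived late was still submitted, and quality is a separate outcome. On the ordinary reading the late rule leaves the submission rate unchanged. The adequacy percentage could shift slightly depending on which samples enter its denominator, but it too is reported descriptively.

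**The case for a change.** The best case for a change is that recorded dates make classification possible but do not supply the rule. The Protocol expects some late samples, since it says the consent form warns of them. Its Background says mindfulness meditation can lower CRP, IL-6 and TNF-α, the markers the spots are meant to measure, so on its own rationale a sample taken after two or three sessions may already be affected. A later RCT would want to know how often mailed collection gives a usable pre-intervention sample, and neither planned rate reports that. One sentence would settle the matter.

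Part of this stands: the day count is right, and the visible text has no rule on time point or counting. The harm, however, depends on a redraw being filed as baseline, which no passage calls for. The secondary outcomes in Measured Outcomes are tied to the self-report measures, and no visible text plans a comparison of cytokines with baseline, so no planned estimate would be contaminated. Anyone who wants the number of in-window samples can get it from dates already collected.

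Lateness should also be uncommon. It takes a neglected 24-hour mailing instruction or a postal delay of about two weeks, despite contact with the research assistant at mailing and at receipt. Nothing bars staff from asking for another sample earlier if one fails to appear. The share of sessions completed before a redraw describes exposure; it does not measure a change in any planned outcome.

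**Conclusion.** No change to the plan is called for. The timing mismatch is real for originals collected in window: a redraw comes at least 8 days outside the baseline or post-intervention week. The silence on placing and counting it is a gap that analysts would fill sensibly: assign the redraw by its actual collection date, do not call it baseline once sessions have started, and count the participant once for submission. The data for this are already recorded. On the ordinary reading the effect on the submission rates is nil, and no test, sample size or visible decision rule is involved.

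This rests on three assumptions. The original was collected inside its window. Late receipt is infrequent, which the mailing instructions support but the documents do not quantify. The text not available here (an earlier part of the SAP, Figure 1 and the consent form) does not direct that redraws be filed as baseline or plan an analysis of change in the markers. If such an analysis were planned, the time point given to a redraw would matter more.
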